
Concomitant Medications/Therapies
	
Oral prednisone or equivalent oral corticosteroid (up to 10 mg daily) and N-acetylcysteine (NAC) (up to 1800 mg daily) are allowed.
 
Medications that, in the opinion of the Investigator, are required for the treatment of acute exacerbations of IPF during the Treatment Period are acceptable.
 
Female subjects of childbearing potential and male subjects with female partners of childbearing potential are required to use double barrier contraception methods during the conduct of the study and for 3 months after the last dose of study drug.

Investigational Product, Dose, and Mode of Administration
	
FG-3019 is a fully human IgG1 kappa monoclonal antibody that binds to connective tissue growth factor (CTGF). It will be administered at a dose of 30 mg/kg by IV infusion in a total volume of 250 mL (up to 400 mL if necessary) normal saline every 3 weeks.

Reference Therapy (and/or Placebo), Dose, and Mode of Administration
	
Placebo (identical to the FG-3019 vehicle) will be handled and administered in a manner that is identical to FG-3019.

Safety Endpoints and Assessments
	
 
• Adverse events and serious adverse events (SAEs)
 
• Laboratory test abnormalities
 
• 12-lead ECGs
 
• Physical examinations
 
• Human anti-human antibodies (HAHA)
 

Efficacy Endpoints and Assessments
	
Primary efficacy endpoint
 
 
• Change from baseline in FVC (percent of predicted value) at Week 48.
 
 
Secondary efficacy endpoints
 
 
• Change in pulmonary fibrosis score by quantitative HRCT at Week 24, Week 48, and later time points.
 
• Change from baseline in HRQoL at Week 24, Week 48, and later time points.
 
• Progression of IPF, defined as time from Day 1 to any one of the following:             
 
○ Death from any cause
 
○ Absolute decline FVC percent of predicted value of <math>\geq 10\%</math> not due to intercurrent illness, confirmed by repeat spirometry
 
 
 

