Acute exacerbations of IPF, characterized by worsening dyspnea over one month or less, new diffuse lung infiltrates and ground-glass opacities on HRCT, and worsening hypoxemia in the absence of pulmonary infection or other identifiable causes, punctuate the natural course of the disease, especially in its pre-terminal phase (Collard, 2007, Hyzy, 2007, Kim, 2006, Walter, 2006). These exacerbations are often fatal events (Hyzy, 2007, Kim, 2006, Martinez, 2005). The etiology of acute exacerbations of IPF is unknown, and its pathogenesis is not well understood (Collard, 2007). IPF-related exacerbations occurred at a rate of 0.13 per person-year in the Olmstead County population-based study reported above (Fernandez Perez, 2010). A less common, rapidly progressive form of IPF, which is common in actively smoking males, has been described (Selman, 2007).

The diagnosis of IPF is suspected when the clinical and radiographic features described above occur in a patient with no known risk factors for interstitial disease and after other types of idiopathic interstitial pneumonias have been excluded. Transbronchial lung biopsy and bronchoalveolar lavage are occasionally performed to rule out other causes of lung infiltrates. The diagnosis of IPF is confirmed when HRCT demonstrates definite features of “usual interstitial pneumonia” (UIP) (subpleural, reticular infiltrates with basal predominance, honeycombing, and absence of the features suggesting a different diagnosis) in the appropriate clinical setting (Raghu, 2011). Surgical lung biopsy, long considered the gold standard for diagnosis of IPF, is now performed in a minority of cases because of the morbidity associated with the procedure and increasing acceptance of diagnosis by HRCT (Raghu, 1999). Nevertheless, combined clinical, radiologic, and pathologic correlation is recommended as the optimal approach to diagnosis.

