The histopathologic pattern of UIP is a heterogeneous, patchy involvement of lung parenchyma with areas of relatively normal lung tissue adjacent to areas that display architectural distortion (“spatial heterogeneity”), infiltrates of fibroblasts and myofibroblasts, collagen deposition, honeycombing, Type II pneumocyte hyperplasia, smooth muscle hyperplasia, and buds of young proliferating fibroblasts adjacent to alveoli called “fibroblastic foci” (Raghu, 2011, Selman, 2006, Visscher, 2006). These histopathologic features are more commonly found in subpleural regions in the lower lung zones. Interstitial infiltrates of lymphocytes and plasma cells are usually not prominent (Visscher, 2006).

Pirfenidone and nintedanib are approved drugs for the treatment of IPF. In addition to these drugs, IPF patients are usually managed with supportive measures such as symptomatic treatment of cough and dyspnea, supplemental oxygen for hypoxemia, smoking cessation, pulmonary rehabilitation, and prophylaxis and control of respiratory tract infections (Idiopathic pulmonary fibrosis: diagnosis and treatment. International consensus statement. American Thoracic Society (ATS), and the European Respiratory Society (ERS), 2000, Walter, 2006, Wuyts, 2009). Corticosteroids and the immunosuppressive drugs cyclophosphamide and azathioprine were commonly prescribed for IPF in the past, but there is no evidence that these drugs improve patient outcomes or alter the natural course of the disease (Collard, 2004, Walter, 2006). Furthermore, IPF subjects taking a combination of prednisone, azathioprine, and N-acetylcysteine (NAC) in one arm of a three-arm multicenter Phase 3 clinical trial experienced increased risks of hospitalization and death compared with those taking NAC only or placebo only (Raghu, 2012). A recent multicenter Phase 3 randomized trial of warfarin in patients with progressive IPF was stopped because of increased mortality in subjects taking warfarin compared with those taking placebo (Noth, 2012). Lung transplantation is the only treatment that improves survival (Noth, 2007, Walter, 2006), but most IPF patients are not eligible for transplantation because of their age or comorbid conditions.

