## 4.6 Concomitant Medications, Procedures and Nondrug Therapies

### 4.6.1 Concomitant Medications

Concomitant medications (any prescription and/or over-the-counter [OTC] preparation) and procedures or nondrug therapies (e.g., physical therapy, acupuncture, continuous positive airway pressure [CPAP]) used by a subject while participating in this clinical trial must be recorded from Screening Visit 1 through the End-of-Study (EOS) Visit.

Other than the restrictions that follow, concomitant medications may be given at the discretion of the Investigator. It is expected that Investigators will provide optimal medical management of idiopathic pulmonary fibrosis and that subjects may be treated with concomitant medications for their various medical conditions. Optimal medical care must be provided, and Investigators should ensure, for example, that subjects maintain stable vital signs and laboratory test values during the course of the study.

Oral prednisone or equivalent oral corticosteroid (up to 10 mg daily) and NAC (up to 1800 mg daily) will be allowed during the study.

Prohibited medications include approved or investigational agents for the treatment of interstitial lung diseases including IPF. The list of prohibited concomitant medications for treatment of IPF includes, but is not limited to, the following: sildenafil, pirfenidone, nintedanib, azathioprine, cyclophosphamide, cyclosporine, interferon gamma 1b, D penicillamine, methotrexate, leflunomide, colchicine, bosentan, ambrisentan, aminobenzoate, mycophenolate mofetil, imatinib, relaxin, etanercept, adalimumab, infliximab, anakinra, abatacept, and rituximab. If sildenafil is used for erectile dysfunction the dosage regimen should be no more than three times a week. Immunosuppressives and monoclonal antibodies used for other diseases such as rheumatoid arthritis are allowed but the indication should be clearly documented. Indications for concomitant medications should be clearly documented in the subjects clinical record (use for IPF or other diseases).

Any medications to treat IPF should be terminated within 5 half-lives of Day 1 dosing. If monoclonal antibodies are used the last dose must be at least 4 weeks before Day 1 dosing (Exclusion criterion 15).

Questions about concomitant medications should be addressed to the attention of the FibroGen Medical Monitor or designee.

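### Section 4.6.1 lets a subject on azathioprine for a non-IPF disease also take the allowed oral corticosteroid and NAC, a combination the protocol's Introduction links to harm in IPF

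*Protocol*

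**What the plan says.** Protocol Section 4.6.1 contains four relevant statements.

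- Corticosteroid and NAC: "Oral prednisone or equivalent oral corticosteroid (up to 10 mg daily) and NAC (up to 1800 mg daily) will be allowed during the study". No condition about other drugs is attached.
- Prohibited drugs: "The list of prohibited concomitant medications for treatment of IPF includes, but is not limited to, the following: sildenafil, pirfenidone, nintedanib, azathioprine", and the list continues. The bar is tied to the IPF indication.
- Exception for other diseases: "Immunosuppressives and monoclonal antibodies used for other diseases such as rheumatoid arthritis are allowed but the indication should be clearly documented".
- A limit on one listed drug outside IPF: "If sildenafil is used for erectile dysfunction the dosage regimen should be no more than three times a week".

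The synopsis repeats the first permission: "Oral prednisone or equivalent oral corticosteroid (up to 10 mg daily) and N-acetylcysteine (NAC) (up to 1800 mg daily) are allowed". It also carries a rescue permission that Section 4.6.1 does not repeat: "Medications that, in the opinion of the Investigator, are required for the treatment of acute exacerbations of IPF during the Treatment Period are acceptable".

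Section 1.1 classes azathioprine as an immunosuppressive. It then describes a three-arm Phase 3 trial with "IPF subjects taking a combination of prednisone, azathioprine, and N-acetylcysteine (NAC) in one arm", and says that these subjects had higher risks of hospitalization and death than subjects in the NAC-alone and placebo-alone arms.

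**The concern.** The Introduction reports a harmful three-drug combination in the disease under study, while the concomitant-medication rules permit that combination in some subjects. The route is narrow: azathioprine must be prescribed for something other than IPF, and the subject must also take both oral corticosteroid and NAC. But every subject in the trial has IPF, and recording a different indication for azathioprine does not change that. What is at stake is the safety of any subject in this position. The protocol allows the combination by an express permission, so this is more than an omitted detail.

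**Working it through.** No figure in the plan bears on this point, so the check is mainly a reading of the rules against one another.

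**Step 1. Is each drug allowed?** All references are to Protocol Section 4.6.1.

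| Drug | Rule | Allowed in a subject with another disease? |
|---|---|---|
| Azathioprine | Barred for IPF; immunosuppressives allowed for other diseases if the indication is documented | Yes |
| Oral prednisone or equivalent | Up to 10 mg daily, no co-medication condition | Yes |
| NAC | Up to 1800 mg daily, no co-medication condition | Yes |

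Section 1.1 itself calls azathioprine an immunosuppressive, so the exception covers it.

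**Step 2. Does any other rule forbid the three together?**

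- Exclusion 15 (Section 5.2) reaches only drugs taken to treat IPF.
- Exclusion 2 mentions vasculitis and connective tissue diseases, but in a criterion that opens with infiltrative lung disease other than IPF. Section 4.6.1 names rheumatoid arthritis as an acceptable reason for immunosuppression, so the exclusion cannot safely be read as removing all such patients. Nor does it cover every use of azathioprine. It narrows the pool without emptying it.
- Exclusion 7 (investigator judgement) and the invitation in Section 4.6.1 to put questions to the Medical Monitor both depend on someone noticing the problem.
- Section 8 removes subjects for a prohibited drug that cannot be stopped, which this is not. It also removes them for adverse events or repeated hospitalizations, but by then harm may have occurred.
- The data monitoring committee (Section 4.8) reviews safety data that have already accrued.
- Footnote g of Appendix 2 sends the reader back to Section 4.6.1, so the position is the same in the extension.

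None of these forbids the combination.

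**Step 3. How many subjects?** The documents give no usage figures, so the proportion *p* taking all three drugs is an assumption. With 136 planned subjects randomized 1:1 (136 / 2 = 68 per arm):

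expected number exposed = 136 × *p*; per arm = 68 × *p*

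| Assumed *p* | Total | Per arm |
|---|---|---|
| 0 | 0 | 0 |
| 0.001 | 0.14 | 0.07 |
| 0.005 | 0.68 | 0.34 |
| 0.01 | 1.36 | 0.68 |

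These are counts of exposed subjects, not of harmed subjects. Section 1.1 gives no event rates, so no risk of harm can be computed.

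**The case against.** The strongest reply is that the evidence is thin and the permission may be deliberate. The support is one background sentence with no dose, duration or rate. Its author-year citation matches only the abstract of the earlier FG-3019 phase 2 study in the reference list, so the trial that showed harm cannot be identified from the documents. Section 4.6.1 lists azathioprine by name, then addresses use in other diseases and sets a separate limit for sildenafil, which suggests that non-IPF use was considered. Leaving another disease to its treating physician is defensible, and the trial supplies none of the three drugs. Investigators have the warning in Section 1.1 and a duty to manage IPF optimally. The safety plan in Section 4.7 and the monitoring committee add further cover.

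Much of this stands, and it limits the weight of the point. It does not remove the point: none of these provisions names the combination, and the sildenafil limit shows that the section can restrict a listed drug outside IPF.

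Three stronger readings are tempting and are not supported.

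- A reader might infer that the permitted doses are known to be harmful. Section 1.1 gives no doses, so harm under the 10 mg and 1800 mg caps is neither shown nor excluded.
- A reader might infer bias between arms or an effect on the FVC result. Nothing in the documents points to either.
- A reader might infer that NAC is the drug to keep, because NAC alone was a comparator. The comparison does not show which component, or which pair, causes the harm.

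**Conclusion.** The point holds in limited form. As written, Section 4.6.1 and the synopsis permit a combination that the protocol itself reports as raising hospitalization and death in IPF, and no other rule closes the gap. The number of subjects affected is unknown and may be zero. The range of 0 to 1.36 subjects rests wholly on the assumed 0 to 1% use. This is a matter of subject safety only, and the change is a low-cost option rather than a condition for the trial to be sound.

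**What to change.** In Section 4.6.1, directly after the sentence allowing immunosuppressives for other diseases, add:

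> Azathioprine, for any indication, must not be taken together with both oral corticosteroid and NAC. None of the three may be started in a subject already taking the other two. A subject taking all three at Screening may be enrolled only if the treating physician judges that one of them can safely be stopped before Day 1. If all three are found in use on study, the Investigator and Medical Monitor agree which to stop; this alone does not require removal from study treatment or loss of scheduled assessments. Corticosteroid for acute exacerbation of IPF is exempt, with the Medical Monitor informed and azathioprine reviewed.

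Add a matching clause to the synopsis after the corticosteroid and NAC permission: but not both together with azathioprine, except corticosteroid for acute exacerbation.

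Reasons for the details:

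- The text names no drug to stop by preference, because Section 1.1 does not identify the harmful component.
- The fourth sentence is needed because a prohibited drug that cannot be stopped leads to removal from treatment under Section 8, where efficacy assessments after withdrawal are discretionary. Without it, endpoint data could be lost.
- The rescue exemption must stand in Section 4.6.1 because only the synopsis now carries that permission. Section 1.1 says of exacerbations: "These exacerbations are often fatal events". Treatment must not be delayed. The cost is that the combination remains possible during rescue.
- The text says oral corticosteroid, slightly wider than the prednisone named in Section 1.1, because Section 4.6.1 permits prednisone or an equivalent as one class.

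The cost is five sentences and one clause. Appendices 1 to 3 need no edit, since their footnotes already refer to Section 4.6.1. On the assumed 0 to 1% use, about 0 to 1.4 subjects would change a drug or not be enrolled. No statistical figure changes.

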### 4.6.2 Contraception

Female subjects of childbearing potential and male subjects with female partners of childbearing potential are required to use double barrier contraception methods during the conduct of the study and for 3 months after the last dose of study drug.

Pregnancy, spontaneous or therapeutic abortion, or events related to pregnancy must be reported (Section 11.3.6).

## **4.7 Safety Plan**

Safety will be assessed throughout the study. A medically complete baseline profile of each subject will be established through medical history, a complete physical examination including vital signs, laboratory tests, PFTs, and a 12-lead ECG. During the course of the study, vital signs, complete and focused physical examinations, laboratory tests, and PFTs will be performed at frequent intervals as described in Appendix 1 and Appendix 2. Any medically significant changes from baseline will be monitored throughout the study and appropriate interventions will be taken accordingly. Safety and tolerability will be monitored closely by FibroGen.

## **4.8 Independent Data Monitoring Committee**

### **4.8.1 Safety Monitoring**

Safety data in this double-blind placebo-controlled study will be monitored on a regular basis by a Data Monitoring Committee (DMC) that is independent of the FibroGen Medical Monitor and Clinical Operations staff. FibroGen is responsible for the establishment of this DMC, the development of a DMC charter, and supporting DMC meetings.

## 5 ELIGIBILITY CRITERIA

FibroGen will not grant waivers to Inclusion Criteria and Exclusion Criteria in this protocol.

### 5.1 Inclusion Criteria

1. Age 40 to 80 years, inclusive.
2. Diagnosis of IPF as defined by current international guidelines (Raghu, 2011). Each subject must have one of the following: (1) *Usual Interstitial Pneumonia (UIP) Pattern* on an available HRCT scan; or (2) *Possible UIP Pattern* on an available HRCT scan and surgical lung biopsy within 4 years of Screening showing *UIP Pattern* (HRCT criteria for *UIP Pattern* and *Possible UIP Pattern* and histopathological criteria for *UIP Pattern* described in Appendix 4).
3. History of IPF of  $\leq 5$  years duration with onset defined as the date of the first diagnosis of IPF by HRCT or surgical lung biopsy.
4. Interstitial pulmonary fibrosis defined by HRCT scan at Screening, with evidence of  $\geq 10\%$  to  $< 50\%$  parenchymal fibrosis (reticulation) and  $< 25\%$  honeycombing, within the whole lung, as determined by the HRCT central reader.
5. FVC percent of predicted value  $\geq 55\%$  at Screening.
6. Female subjects of childbearing potential (including those  $< 1$  year postmenopausal) and male subjects with female partners of childbearing potential, must use double barrier contraception methods during the conduct of the study, and for 3 months after the last dose of study drug.

### 5.2 Exclusion Criteria

1. Female subjects who are pregnant or nursing.
2. Infiltrative lung disease other than IPF, including any of the other types of idiopathic interstitial pneumonias (Travis, 2013); lung diseases related to exposure to fibrogenic agents or other environmental toxins or drugs; other types of occupational lung diseases; granulomatous lung diseases; pulmonary vascular diseases; systemic diseases, including vasculitis and connective tissue diseases.
3. HRCT scan findings at Screening are inconsistent with *UIP Pattern*, as determined by the HRCT central reader (a definition of Inconsistent with *UIP Pattern* is provided in Appendix 4).
4. Pathology diagnosis on surgical lung biopsy is anything other than *UIP Pattern*, as determined by the local pathologist (Appendix 4).
5. The Investigator judges that there has been sustained improvement in the severity of IPF during the 12 months prior to Screening, based on changes in FVC, diffusing capacity of the lung for carbon monoxide (DLCO), and/or HRCT scans of the chest.

6. History of other types of respiratory diseases including diseases or disorders of the airways, lung parenchyma, pleural space, mediastinum, diaphragm, or chest wall that, in the opinion of the Investigator, would impact the endpoints in the protocol or otherwise preclude the subject's participation in the study.
7. History of any other respiratory, cardiovascular, renal, hepatic, metabolic, neurologic, hematologic, or other medical conditions that, in the opinion of the Investigator, would preclude the subject's participation in the study.
8. Clinically important abnormal laboratory tests (including serum creatinine  $\geq 1.5$  x upper limit of normal [ULN], hemoglobin (Hb)  $< 10$  g/dL, white blood cells  $< 3,000/\text{mm}^3$ , platelets less than  $100,000/\text{mm}^3$ , serum total bilirubin  $> 1.5$  x ULN, serum alanine aminotransferase (ALT) or aspartate aminotransferase (AST)  $\geq 2$  x ULN, or serum alkaline phosphatase  $\geq 2$  x ULN).
9. Upper or lower respiratory tract infection of any type within 4 weeks of Screening.
10. Acute exacerbation of IPF within 3 months of Screening (a definition of acute exacerbation of IPF is provided in Section 8).
11. Evidence of obstructive lung disease by any of the following criteria: forced expiratory volume in 1 second/forced vital capacity (FEV1/FVC) ratio  $< 0.70$ , or extent of emphysema on HRCT greater than the extent of fibrosis on HRCT.
12. DLCO  $< 30\%$  of the predicted value.
13. High likelihood of lung transplantation (in the opinion of the Investigator) within 6 months after Day 1.
14. Poorly controlled chronic heart failure; clinical diagnosis of cor pulmonale requiring specific treatment; or severe pulmonary hypertension requiring specific treatment that, in the opinion of the Investigator, would preclude the subject's participation in the study.
15. Use of medications to treat IPF within 5 half-lives of Day 1 dosing. If monoclonal antibodies were used, the last dose of the antibody must be at least 4 weeks before Day 1 dosing.
16. Use of any investigational drugs, including any investigational drugs for IPF, within 4 weeks prior to Day 1 dosing.
17. History of cancer diagnosis of any type in the 3 years preceding Screening, excluding non-melanomatous skin cancer, localized bladder cancer, or in situ cancers.
18. Clinically significant trauma or surgical procedures within 4 weeks prior to dosing.
19. Planned elective surgery during the study including 4 weeks following the final dose of Study Drug.
20. History of allergic or anaphylactic reaction to human, humanized, chimeric or murine monoclonal antibodies.
21. The Investigator judges that the subject will be unable to fully participate in the study and complete it for any reason, including inability to comply with study procedures and treatment, addiction, or any other relevant medical or psychiatric conditions.
22. Body weight  $> 130$  kg.

- 23. Previous treatment with FG-3019.
- 24. Inadequate IV access.

